### **3.4. Unmasking**

Unmasking of treatment assignment is rarely necessary. If adverse events occur that may be related to the study treatment, then the study treatment is stopped and the patient continues follow-up. Envelopes with treatment assignment are provided to the clinic in the case a treating physician feels it is important to know the treatment assignment. In addition, the DCC provides a phone number where authorized personnel can receive unmasking information. All participants are provided with a wallet card that provides information that they are participating in a clinical trial and gives the contact numbers of personnel at the clinic.

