### 3.1. Description of study treatment

Participants will be randomly assigned to receive a daily dose of 150 mg of zinc acetate or matched placebo taken in three doses of 50 mg each or placebo. For this trial 50 mg zinc acetate capsules will be over-encapsulated and a matched placebo will be created. Zinc will be taken with the morning or evening meal. Participants will be instructed to titrate up the dose of study drug starting with one capsule (50 mg) in the morning on day 1, increasing to two capsules (100 mg) on day 4, and reaching three capsules (150 mg) on day 8. Participants will be instructed to take the medication with food. If participants are not able to tolerate the full dose, they may split the dose

into two or three doses per day taken at meal-time (e.g. two capsules in AM and one capsule in PM, or one capsule with breakfast, lunch, and dinner). If a participant is not able to tolerate the full dose, then the dose should be titrated down to the highest tolerable dose, i.e., one or two capsules as tolerated.

The study will use the FDA-approved formulation of oral zinc, Galzin®. FDA has approved Galzin® 150mg/day for long-term use in adults with Wilson's disease. Zinc supplementation for food has been considered Generally Recognized as Safe (GRAS) by the FDA. NIH recommends up to 40 mg/day as a dietary supplement in adults and multivitamins used long-term for prevention of macular degeneration contain 80mg of elemental zinc. OTC lozenges (Cold-eez®) contain 13.3 mg of zinc as zinc gluconate and are taken in doses of up to 80 mg/day for relief of URI symptoms. Zinc gluconate is available as unregulated nutritional supplements in 100mg capsules.

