### 3.3. Side effects

The most common adverse effects of zinc supplementation are dyspepsia, nausea, and a metallic taste. These side effects can be mitigated by downward adjustment of the dose, taking the drug with meals, and/or spreading the dose out over the day (i.e. taking 1 capsule in the morning and 2 capsules at night, or taking 1 capsule each at breakfast, lunch, and dinner).

Elevations of liver and pancreatic enzymes have been reported in patients with Wilson's disease, treated with zinc acetate, but this has not been reported in other populations and the relationship with zinc supplementation is unclear. Participants with a history of pancreatitis will be excluded from the study. Study participants experiencing abdominal pain should be evaluated for possible pancreatitis. With zinc gluconate nasal spray some patients have noted loss of smell, but this has not been reported with oral zinc.

Zinc is listed as a class A drug for pregnancy indicating that it does not have substantial teratogenic potential. We are excluding pregnant and lactating women from this trial because pregnancy may have either beneficial or deleterious effects on chronic cough and zinc is transmitted in breast milk that may alter infant feeding behavior. Women of child bearing potential must be willing to use appropriate methods of pregnancy prevention during the duration of the study. Women of childbearing potential includes all female participants except those who are surgically sterile (both ovaries and/or uterus removed), postmenopausal (no menstrual period for longer than 12 consecutive months), or incapable of pregnancy.

The FDA-approved prescribing information for zinc acetate states the following regarding over-dosage:

"One fatality associated with over-dosage of zinc sulfate has

Confidential, not for attribution or citation.

been reported. The death of this adult woman followed the accidental ingestion of approximately 28 g of zinc sulfate. [Equivalent to 560 capsules of zinc acetate or 3 bottles of dispensed study drug]. Death occurred on the fifth day after ingestion and was attributed to renal failure. Hemorrhagic pancreatitis and hyperglycemic coma resulted from the overdose. The amount ingested was 500 mg/Kg of zinc sulfate, a value that is in the same order of magnitude as that found to be lethal in animals.”

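### Section 3.4 stops study drug for any possibly related adverse event, while sections 3.1 and 3.3 adjust the dose and continue for the same events

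*Combined protocol and SAP*

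**What the plan says.** Three sections of the combined protocol and SAP bear on what a clinic does when a participant has an adverse event on study drug.

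- Section 3.1 (Description of study treatment) sets an upward titration from one capsule on day 1, "increasing to two capsules (100 mg) on day 4, and reaching three capsules (150 mg) on day 8". For intolerance it gives two steps. The first is "If participants are not able to tolerate the full dose, they may split the dose" over the day's meals. The second applies if the full dose still cannot be tolerated: "then the dose should be titrated down to the highest tolerable dose", meaning one or two capsules. Treatment continues under both steps.
- Section 3.3 (Side effects) says: "The most common adverse effects of zinc supplementation are dyspepsia, nausea, and a metallic taste". It then says: "These side effects can be mitigated by downward adjustment of the dose", and adds taking the drug with meals and spreading it over the day. It treats abdominal pain separately: "Study participants experiencing abdominal pain should be evaluated for possible pancreatitis".
- Section 3.4 (Unmasking) opens with "Unmasking of treatment assignment is rarely necessary" and continues: "If adverse events occur that may be related to the study treatment, then the study treatment is stopped and the patient continues follow-up". Provisions for treatment-assignment envelopes, a telephone number for unmasking and a wallet card follow.

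Section 4.1 (Primary Analysis) makes tolerability of zinc against placebo the focus. It is judged by qualitative assessment of adverse drug effects and by unadjusted comparison of event frequency and adherence between arms.

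**The concern.** Dyspepsia, nausea and metallic taste are named in 3.3 as effects of zinc. In a masked trial, any participant who reports one of them has an event that could be due to study drug, so the condition in 3.4 is met. Read literally, 3.4 then removes the drug, whereas 3.1 and 3.3 keep the participant on it at an adjusted dose.

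Tolerability is the first of the study aims in section 2 and the focus of the primary analysis. Whether a participant with nausea is stopped or moved to one or two capsules determines later exposure, measured adherence and time at risk on drug. A reader of the tolerability result needs to know which rule produced it. A zinc arm in which many participants stopped means one thing if stopping was required at the first related event, and another if it happened only after dose reduction failed.

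**Working it through.** No arithmetic decides this point. The check sets the rules side by side, looks for a rule of precedence, and asks which parts of the analysis depend on the answer.

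1. **Trigger.** Section 3.4 applies to adverse events possibly related to study treatment and names no grade, seriousness criterion or event type. Section 3.1 applies to inability to tolerate the full dose. Section 3.3 applies to the listed common effects. An episode of nausea that makes three capsules hard to take satisfies all three.

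2. **Response.** Section 3.4: stop the drug and keep following the participant. Section 3.1: split the dose, or lower it to the highest tolerable level. Section 3.3: lower, spread or take with meals. For the same event, 3.4 ends treatment and the other two continue it.

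3. **Precedence.** Section 3.4 does not refer to 3.1 or 3.3, and they do not refer to it. The visit lists in 2.4 only have staff assess adverse events and, at the week 1 call, review adherence. The monitoring plan in section 6 covers reporting, review by the medical monitor and review by the DSMB. Neither gives a discontinuation criterion or a severity threshold.

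4. **Timing.** The week 1 telephone visit falls at about the time the third capsule is added on day 8. If intolerance appears as the dose rises, the two rules meet early, with most of the six weeks still to run.

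5. **What depends on the rule.** A participant's first possibly related event happens before either rule is applied, so its occurrence and timing are unaffected. What can differ is later capsule intake (hence adherence), later events, and the serum zinc and copper measured at week 6.

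6. **What does not depend on it.**
   - The sample-size statement in 4.1 uses 18 per arm, 0.56 SD, a one-sided type 1 error of 0.20 and 80% power. The stopping rule is not an input. Those inputs give power of 0.799 by the normal approximation and 0.797 by the noncentral t, so the stated 80% stands.
   - Assignment is masked and stratified by clinic, so either rule would be applied without knowledge of arm.
   - Follow-up continues after stopping, and 4.1 includes all data from all randomized participants. Literal stopping would lower exposure in the zinc arm and so change the exposure that the comparison reflects. It would not invalidate the comparison.

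**The case against.** The strongest reply is that the 3.4 sentence has been read out of its setting. It stands under a heading about unmasking, between the remark that unmasking is seldom needed and the arrangements for envelopes. Its evident purpose is to explain why the code need not be opened. Dose management belongs to 3.1 and side-effect management to 3.3. Both are more specific, and a reader may let the specific rule override the general one. The week 1 call to deal with adherence problems, and the worked split-dose examples, would have almost nothing to do if every possibly related event ended treatment.

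Most of this is persuasive about intent, and the intended rule is fairly clear. It does not alter the text. Section 3.4 neither confines itself to serious events nor points to the titration rules, and an instruction to clinics should not depend on inferring its purpose from the heading.

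The reply also limits how far the point can go. A reader might infer that clinics would in fact diverge, or that participants would be taken off drug at the first nausea. The documents show neither. A reader might also infer that dose changes go unrecorded. Section 2.6.3 lists adverse events and medication use among the data assessed, unused capsules are returned at V5, and the case report forms are not among the documents, so no gap in data collection can be claimed. It is also tempting to size the problem with capsule counts from the titration schedule. The plan gives no event rate and no definition of adherence, so such counts would describe one hypothetical participant against an assumed denominator. None are given here.

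**Conclusion.** Wrong as written; minor. Section 3.4 states an unqualified stopping rule that conflicts with 3.1 and 3.3 for the events that the primary tolerability analysis will mainly count. It is a conflict between stated rules, not a missing detail.

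The conclusion rests on the literal wording and on the absence of any precedence rule in the documents supplied. A manual of procedures might already settle the matter; none is included. The practical size cannot be put in numbers from the documents.

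A stronger reading, that the conflict undermines the trial's power, masking or efficacy comparison, is not supported, for the reasons in the last step of the working. Nor does it threaten the go/no-go decision by itself, because 4.1 rests that on a synthesis of feasibility, tolerability and the size and consistency of the treatment effect. What is at stake is how clearly the tolerability and adherence results can be interpreted.

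**What to change.** Replace the 3.4 sentence with wording that separates stopping from dose adjustment, for example:

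> Study treatment is stopped, without unmasking, for possibly related adverse events that are serious or severe, for suspected pancreatitis, for intolerance that persists at one capsule per day, or at the study physician's judgment; follow-up continues. Other possibly related adverse events that reflect intolerance are managed first by splitting or reducing the dose as in 3.1 and 3.3.

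Putting the stopping conditions first makes the precedence explicit. Defining the second group by intolerance, and not by a list of symptoms, brings in effects that 3.3 does not name, such as vomiting. Severe nausea can lead directly to stopping. Abdominal pain is still evaluated as 3.3 requires, and drug is stopped if pancreatitis is suspected. The protocol text does not grade adverse events, so the term severe should be tied to any grading used on the forms or left to the study physician.

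Optionally, report by arm the numbers on full dose, on reduced dose and stopped at week 6. This would help interpretation but is not needed to resolve the conflict.

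The cost is a short amendment and a notice to sites. Sample size, visits and analysis model do not change.

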## **4. Analysis plan**

---

### **4.1. Sample size**

The primary goals of the pilot study are to establish the feasibility of performing a randomized trial and to obtain preliminary estimates of the relative efficacy of zinc versus placebo and the statistical properties of the patient reported outcome measures. A sample size of 36 (18/arm) has 80% power to detect a treatment effect of 0.56 standard deviations (SD) or greater, where SD is for the difference from baseline to 6 weeks in CQLQ score, based upon a two-sample t-test and a one-sided type 1 error rate of 0.20. We are conducting a contemporaneous cohort study to establish the minimal important difference (MID) and SD for change in CQLQ scores in 100 participants with chronic cough. This analysis will not necessarily provide information whether the changes are clinically important, but will provide a framework for establishing changes that are outside of the range of variability of symptoms and would be noticeable by the patient. Thus, in

this context, the MID would be analogous to the “Just Noticeable Difference” (JND) used in psychophysics of perception.

### Primary Analysis

The primary analysis will focus on the tolerability of zinc acetate versus placebo. These analysis will rely on qualitative assessments of adverse drug effects as well as unadjusted comparisons of the frequency of events and adherence by treatment assignment.

The statistical analysis for efficacy will be an unadjusted comparison of 6-week change in CQLQ between treatment groups. A linear mixed effects model will be used to model change in CQLQ over time. A saturated means model with indicators for each time point, treatment and treatment by time interaction, will be specified and a random effect for individual will be used to account for the repeated measurements over time. The 6-week treatment by time interaction term represents the difference in change in CQLQ between the treatment groups, i.e. the primary outcome. If the data are non-normal, then transformations and non-parametric alternatives (e.g. Wilcoxon Rank-Sum test comparing the raw differences from baseline to 6-weeks between treatment groups) will be explored. Using the methods described by Cocks and Torgerson, we will test whether or not the upper boundary of the 1-sided 80% confidence interval of the treatment effect excludes the MID. For example, a total sample size of 36 would be sufficient to exclude a MID of 5 or higher for a 1-sided 80% confidence interval if the standard deviation for the change in CQLQ was 15. Sensitivity analyses using alternate mean and covariance structures will also be performed. Analyses will be done based upon principles of intention to treat, i.e. all data from all randomized participants will be included in the analysis.

Secondary outcomes include, but are not limited to, LCQ, diary data, C-VAS, GACC, quality of life measures, and safety data. Continuous variables will be analyzed similarly to the primary outcome. Event outcomes will be analyzed in two ways: negative binomial regression for rates and Kaplan-Meier curves and Cox proportional hazards models for time to first event.

Assessment of futility for a definitive trial will not rest with any single measure but will depend on a synthesis of the overall study feasibility and treatment tolerability as well as magnitude and consistency of the observed treatment effect. However, in line with formal futility designs in neuroscience and oncology, we will not likely proceed with a definitive trial if the upper boundary of the one-sided 80% confidence interval of the treatment effect excludes the minimally important difference for the CQLQ, which we will validate in the concurrent cohort study.

Descriptive statistics will be computed for baseline clinical and demographic characteristics by treatment group. Results will be displayed as means with standard deviations, medians with 1st and 3rd quartiles, and proportions as appropriate.

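### The efficacy bound that informs go/no-go comes from an unadjusted random-intercept model; an unstructured covariance would keep its error rate near nominal, and adjusting for baseline CQLQ would usually tighten it, at no data cost

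*Combined protocol and SAP*

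**What the plan says.** The Primary Analysis section gives tolerability the main role: "The primary analysis will focus on the tolerability of zinc acetate versus placebo". For efficacy it states: "The statistical analysis for efficacy will be an unadjusted comparison of 6-week change in CQLQ between treatment groups". The model has saturated means (visit, treatment and their interaction), and "a random effect for individual will be used to account for the repeated measurements over time". The effect is read from the week-6 interaction. On other models the section says only: "Sensitivity analyses using alternate mean and covariance structures will also be performed". It also commits to intention to treat: "all data from all randomized participants will be included in the analysis".

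Section 4.1 bases power on a different calculation, "where SD is for the difference from baseline to 6 weeks in CQLQ score, based upon a two-sample t-test", with one-sided alpha 0.20 and 18 per arm.

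The futility paragraph says no single measure will decide. It then takes the CQLQ MID as the value that may be ruled out, and says: "we will not likely proceed with a definitive trial if the upper boundary of the one-sided 80% confidence interval of the treatment effect excludes".

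Baseline CQLQ is collected at Visit 2 (section 2.4), and assignments are released only after baseline evaluations are complete (section 3.2).

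**The concern.** Two features of the model affect the bound, and they should be kept apart.

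**Precision.** Baseline CQLQ enters only as the week-0 outcome, with a free treatment difference at week 0. With complete data the week-6 interaction is then exactly the raw difference in mean change. Randomisation makes the baseline means equal in expectation, and the model does not use that.

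**Calibration.** A single random intercept imposes one variance and one correlation on all four visits, so off-treatment week-8 data help set the standard error of the on-treatment week-6 contrast. If the assumption fails, the 80% bound does not have an 80% coverage rate. The t-test on change in section 4.1 makes no such assumption. With complete data an unstructured covariance reproduces that t-test (34 df); the random intercept has the same standard error in expectation only when variances and correlations are equal.

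The bound is the one formal numerical criterion named for not proceeding. If it is too narrow, a treatment whose true effect equals the MID is set aside more often than the plan intends; if too wide, the pilot discriminates less than it could. The sensitivity analyses do not settle this. They are unnamed, baseline adjustment is not mentioned, and nothing says which result feeds the futility criterion.

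**Working it through.** **Inputs.** 18 per arm, one-sided alpha 0.20, effect 0.56 SD of change (section 4.1). MID 5 and change SD 15 (worked example in Primary Analysis). Score SD 12-15 and ICC 0.89 (section 2.6.1). Visits at weeks 0, 3, 6 and 8 (section 2.5). The correlation rho between baseline and week 6 is not given.

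**The plan's figures.**
- Noncentral t, 34 df: power at 0.56 SD = 0.797. Reproduced.
- SE = 15 × √(2/18) = 5.00; bound distance = 0.852 × 5.00 = 4.26, below 5, so the worked example holds for an observed effect of zero.
- Chance of excluding an MID of 5 when the true effect is zero: 0.561.

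**Precision.** With r = SD at week 6 / SD at baseline, and complete data,

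SE ratio (adjusted / change score) = √[ r²(1 − rho²) / (1 + r² − 2·rho·r) × 33/32 ].

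The factor 33/32 = 1 + 1/(36 − 4) is the cost of estimating the slope. For r = 1 the first part is (1 + rho)/2.

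| rho (r = 1) | SE ratio | Power at 0.56 SD, change SD 15 |
|---|---|---|
| 0.89 | 0.987 | 0.803 |
| 0.70 | 0.936 | 0.827 |
| 0.50 | 0.879 | 0.855 |
| 0.22 | 0.793 | 0.897 |

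The two ends are alternative readings of the documents and cannot both hold:
- rho = 1 − 15²/(2·SD²) gives 0.22 for score SD 12 and 0.50 for score SD 15.
- If rho were the ICC of 0.89, the change SD would be 12·√0.22 = 5.6 to 15·√0.22 = 7.0, not 15.

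Unequal SDs matter. For r = 1.25 the ratios are 0.960 (rho 0.50), 1.006 (0.70), 1.016 (0.80) and 0.996 (0.89). For r = 0.8 (SD 15 falling to 12) the gain is about 19% to 30%.

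Ceiling on the loss: the residual variance is the minimum over b of Var(Y6 − b·Y0), so it cannot exceed Var(Y6 − Y0). The mean ratio is therefore at most √(33/32) = 1.0155, reached when the slope is 1.

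**Calibration.** The random-intercept SE targets √[(4/18) × (mean visit variance − mean between-visit covariance)]. The true SE of the contrast is √[(2/18) × Var(change)]. At a true effect equal to the MID, the false-stop rate is about Φ(−0.845 × model SE / true SE). Score SD is 15 unless stated; simulations used 100,000 runs per pattern.

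| Assumed pattern | Model SE | True SE | False stop, formula | Simulated |
|---|---|---|---|---|
| Exchangeable, 0.5 | 5.00 | 5.00 | 19.9% | 19.8% |
| Serial decay, 0.5 at 6 weeks | 4.41 | 5.00 | 22.8% | 23.0% |
| Baseline-post 0.5, post-post 0.8 | 4.18 | 5.00 | 24.0% | 24.2% |
| Baseline-post 0.7, post-post 0.5 | 4.47 | 3.87 | 16.5% | 16.3% |
| Week-8 SD 20, correlation 0.5 | 5.53 | 5.00 | 17.5% | 17.7% |
| Post-baseline SD 18.75, correlation 0.5 | 6.00 | 5.73 | 18.8% | 19.0% |

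Example, third row: mean correlation (3 × 0.5 + 3 × 0.8)/6 = 0.65; 225 × 0.35 = 78.75; √(78.75 × 4/18) = 4.18.

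The unadjusted unstructured bound gave about 20% in every pattern, so this gain comes from the covariance and not from adjustment. In the serial and unequal-correlation rows the planned mean half-widths (3.71 and 3.52) are too narrow against a valid unadjusted 4.23. The adjusted half-width of 3.72 is valid there but no tighter than the planned one.

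**Recommended model at n = 36.** REML, constrained baseline means, unstructured covariance, Kenward-Roger, three clinics with an assumed 6 per arm each; 10,000 runs per complete-data case and about 8,000 per missing-data case.
- Five complete-data patterns: false stop 19.9-20.7%.
- Three patterns with an assumed 3 of 18 per arm lost after week 3 (rho 0.5; exchangeable, serial, unequal): 20.6%, 20.2% and 19.9%, against 20.7%, 22.7% and 22.6% for the planned model.
- True SE in those three: 4.82, 4.72 and 4.59 against 5.35, 5.27 and 5.15, or 10-11% smaller.
- All 74,304 fits converged.

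**The case against.** The strongest reply is that this is a choice between valid estimators. The planned one is unbiased and matches both the sample-size basis and the rank-sum alternative on raw differences. The plan already promises other mean and covariance structures. Tolerability comes first, and futility rests on several inputs. All of this stands, and it is why the point is an improvement. It does not remove the gap: the plan does not say which bound feeds the criterion, and choosing after unmasking would invite selection.

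The size of the precision gain is also uncertain. The 21% pairs the lowest score SD with a change SD offered only as an example, while the ICC, whose interval is not stated, points to about 1%. Entry requires a cough VAS of at least 30, so SDs may widen after baseline and shrink the gain. This stands too. The answer is the asymmetry: possible gains are large, and the mean loss is capped at 1.6%.

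The miscalibration rests on assumed patterns, and its direction is unknown. True; some patterns make the bound conservative. The unstructured model removes the dependence either way.

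Finally, visit SDs and correlations could be tabulated without changing the model, and the REML runs did not include the larger week-8 SD. Both are fair limits; neither affects the case for the change.

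**Conclusion.** The point holds as a worthwhile improvement to the efficacy part of the plan; it is not a flaw that invalidates it.

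- **Calibration:** the planned bound's false-stop rate at the MID ranged from about 16% to 24% across the assumed patterns, against a nominal 20%. It is correct if visits are exchangeable. An unstructured covariance kept it near 20% throughout.
- **Precision:** with equal SDs, adjustment lowers the true SE by about 1% to 21%, depending on a correlation the documents do not give. At 0.89 the gain is negligible; at 0.22-0.50, which follows from pairing the score SDs with a change SD of 15, it is 12% to 21%. On that reading the chance of excluding an MID of 5 under no effect rises from 56% to 61-66%.

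The figures assume 18 complete per arm except where loss is stated, and normal data. The protocol states no dropout allowance.

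**What to change.** Pre-specify one model as the efficacy analysis and as the sole source of the bound in the futility paragraph:

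- a longitudinal model of CQLQ at weeks 0, 3, 6 and 8, with baseline means constrained equal across arms;
- unstructured covariance and Kenward-Roger degrees of freedom;
- clinic included because it is the randomisation stratum (no precision gain is claimed for it).

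Name week-6 ANCOVA on baseline CQLQ as the fallback if the model does not converge. Keep the current unadjusted random-intercept model as a named sensitivity analysis. Report the estimated visit SDs and correlations, which also serves the stated aim of assessing the statistical properties of the cough measures.

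The concurrent cohort in section 4.1 is to give an "SD for change in CQLQ scores in 100 participants with chronic cough". Combined with that cohort's score SDs, this yields rho, so the expected gain can be stated before unmasking.

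Cost: analysis-plan wording only, with no new data or visits. The model spends about three degrees of freedom (one for baseline, two for three clinics) and estimates ten covariance parameters instead of two. The mean precision loss from the baseline covariate is at most 1.6%.
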